10.53 Grade 5 AEs (Death)

10.531 Any death within 30 days of the patient's last study treatment or procedure regardless of attribution to the study treatment or procedure

10.532 Any death more than 30 days after the patients last study treatment or procedure that is felt to be at least possibly treatment related must also be submitted as a Grade 5 AE, with a CTCAE type and attribution assigned.

10.6 Monitoring and Auditing

The investigator will permit study-related monitoring, audits, and inspections by the IRB, the sponsor, and government regulatory agencies, of all study related documents (e.g. source documents, regulatory documents, data collection instruments, study data etc.). The investigator will ensure the capability for inspections of applicable study-related facilities (e.g. pharmacy, diagnostic laboratory, etc.).

Participation as an investigator in this study implies acceptance of potential inspection by government regulatory authorities and applicable compliance offices

10.61 Medical Monitoring

It is the responsibility of the Principal Investigator to oversee the safety of the study at his/her site. This safety monitoring will include careful assessment and appropriate reporting of adverse events as noted above, as well as the construction and implementation of a site data and safety-monitoring plan (see section 10.5 “Monitoring and Auditing”). Medical monitoring will include a regular assessment of the number and type of serious adverse events. Any serious adverse events will be followed up by the sentinel event reporting procedure.

10.62 Internal Data and Safety Monitoring Board

The trial will be reviewed by the Radiation Oncology Research Executive Board on a yearly basis to assess accrual, adverse events, and any endpoint problems. Any safety issues requiring protocol changes will be communicated through protocol amendments. The Mayo Clinic Cancer Center (MCCC) Data Safety and Monitoring Board (DSMB) is responsible for reviewing the accrual and safety for this trial at least twice a year, based on reports provided by the MCCC Statistical Office..

11.0 Treatment Evaluation

11.1 Patients will be evaluated at baseline, then according to the Assessment Schedule (Section 4.0)

11.2 At the time of reevaluation, patients will be classified in the following manner:

11.2.1 No evidence of disease (NED).

11.2.2 Recurrence of disease (REC). Recurrence must be confirmed by biopsy.

11.2.3 The site of recurrence (or failure) will also be collected and classified as local vs. regional vs. distant recurrence. The specific site of failure will also be collected as well.

11.2.4 Secondary Treatment. The date of the first retreatment and extent of retreatment post-recurrence (i.e. secondary resection or re-irradiation for primary disease), will be collected. Pathology, if available, and operative reports are required to be submitted per Section 18.0.

11.3 Cosmesis evaluation and Patient Reported Outcomes

11.3.1 Digital photographs should be performed according to the schedule outlined in section 4.0 and should include three poses: from the front with hands on hips, both oblique and lateral views with hands behind the back. Recommended framing should go from the sternal notch to the umbilicus. If possible, patients should be photographed against a solid colored background such as a white sheet.

11.3.2 The Breast Cancer Treatment Outcome Scale (BCTOS) is a self-report instrument that has high reliability and validity and will be used for evaluating patient-rated cosmesis according to the schedule outlined in section 4.0.

11.3.3 The 4 point (excellent, good, fair, poor) adaptation of the Harvard Cosmesis Scale will be used by nursing staff to grade cosmesis in women who undergo reconstruction.

11.4 Patient-Reported Outcomes Version of the Common Terminology Criteria for Adverse Events (PRO-CTCAE) will be used for patient self-reporting of toxicities in the CTCAE.
Other Patient Reported Outcome questions (fatigue, pain, arm function etc.)
Unplanned surgical intervention and Reconstruction Failure will be adjudicated by a plastic surgeon and a general surgeon.

***Note the Outcomes assessments will be collected through clinical mechanisms by the Mayo Clinic Radiotherapy Patient Outcomes Registry and Biobanking study These will then be correlated with analysis from this study.**

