4.0 Test Schedule

Assessments, tests and procedures	Treatment			Observation ⁷
	Baseline ²	Last day of treatment (+/- 2 days)	12 weeks (+/- 8 weeks) post-radiation	12 months (+/- 3 month) post completion of radiotherapy, 24 months (+/- 3 months), 36 months (+/- 3 months), and at 5 years (+/- 3 months)
History and Physical exam (including breast assessment/exam) ¹	X	X	X	X
Mammogram	X ¹⁰			X ¹¹
Cosmesis ,QOL Outcome Assessment and Breast-Q ¹⁶ (see section 11.3 and Appendix)	X ¹³	X	X	X
Digital Photograph	X	X	X	X
Review of surgical specimen(s) to confirm eligibility	X ³			
Echocardiography ^{9, 14}	X ¹³			X ⁸
Radiation toxicity assessment (see section 10.4)	X	X	X	X
Serum pregnancy test	X ⁴			
Blood specimen ^{5, 17, R}	X ¹⁵	X	X	X ¹²
Surgical tumor specimen ^{6, 18, R}	X			

1. A general history & physical must be done \leq 8 weeks prior to registration. This should include an assessment of ECOG performance status (see Appendix I).

2. Following definitive surgical resection and adjuvant chemotherapy if indicated, prior to the start of radiation.
3. Outside pathology must be reviewed at the treating institution.
4. For women of childbearing potential only, must be within 7 days of radiotherapy
5. See section 14 for collection time and preparation of samples
6. See section 17 for collection time and preparation of samples
7. Patients that cannot come back to Mayo Rochester within the time constraints of the follow-up schedule; efforts to obtain outside records and send QOL's to be completed will occur, however the required items may not be captured.
8. Ideally 6-12 months post radiotherapy in HER2 positive patients treated with HER2 directed therapy and in patients treated with anthracycline as part of routine clinical care. Only followed for Echos 1 year post therapy.
9. Co-enrollment on IRB 15-007443 (echo protocol) is required in Rochester while open
10. Completed \leq 12 months prior to study entry
11. As clinically indicated
12. At 12 months post-treatment visit only to coincide with echocardiography.
13. Should be \geq 14 days since last chemotherapy
14. After closure of IRB 15-007443 (echo protocol) echocardiography tests will be performed only in left sided patients previously treated with anthracycline and/or HER2 directed systemic therapy. This correlative component will occur at Rochester Mayo only.
15. Baseline blood collection will be drawn through co-enrollment on IRB 15-000136 (Radiation Oncology Outcomes Registry and Biobanking Study).

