16.62 Secondary Analyses

16.621 *Acute adverse events (up to 90 days post-RT):* All patients who were registered to the study and started treatment will be included in the acute adverse event analysis. An acute adverse event is an AE, regardless of attribution, that occurs up to 90 days post-RT. The maximum grade for each type of acute AE will be recorded for each patient. Data will be summarized as frequencies and relative frequencies by treatment arm. Additionally, the relationship of the adverse event(s) to the study treatment will be taken into consideration.

16.622 *Late adverse events and reconstruction failure:* All patients who were registered to the study and started treatment will be included in the late adverse event and reconstruction failure analysis. A late adverse event is an AE, regardless of attribution, that occurs at least 90 days post-RT and up to 5 years post-RT. The maximum grade for each type of late AE will be recorded for each patient. Data will be summarized as frequencies and

relative frequencies by treatment arm. Additionally, the relationship of the adverse event(s) to the study treatment will be taken into consideration.

- 16.623 *Quality of life*: The subscales of the BCTOS, elements from CTCAE-PRO, and other patient reported measures such as fatigue, breast pain, breast shape, and arm related morbidity outlined in the appendix will be summarized as the mean \pm SD and median (minimum value, maximum value). Changes in the QOL measurements from baseline will be determined at each follow-up visit and measured by treatment arm. The comparison of the changes at each time point between the two treatment arms within each cohort will be done with a paired t-test or Wilcoxon signed rank test, whichever is appropriate.
- 16.624 *Cosmesis*: The values of the cosmesis instruments (patient self-reported and panel-assessed) will be summarized with the frequencies and confidence intervals of fair or poor cosmesis events at baseline, 2 years, and 5 years by treatment arm.
- 16.625 *IBTR incidence*: The IBTR cumulative incidence will be estimated using a competing risks method (Gooley et al.) by treatment arm. The competing risks will be regional/distant breast cancer recurrence and death.

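### Quality-of-life change is compared between arms separately at each of six post-baseline visits, with no key visit, baseline adjustment or longitudinal model; the chance of a false-positive visit is about 20% per scale

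*Combined protocol and SAP*

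**What the plan says.** **Collection.** The section 4.0 row headed "Cosmesis ,QOL Outcome Assessment and Breast-Q" is marked at baseline, on the last treatment day, at "12 weeks (+/- 8 weeks) post-radiation", and at "12 months (+/- 3 month) post completion of radiotherapy, 24 months (+/- 3 months), 36 months (+/- 3 months), and at 5 years". That makes six post-baseline visits. Footnote 16 confines Breast-Q to the observation visits, so Breast-Q has no baseline. Section 11.3.2 states that the BCTOS "will be used for evaluating patient-rated cosmesis according to the schedule outlined in section 4.0".

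**Quality-of-life analysis.** Section 16.623 covers the BCTOS subscales, PRO-CTCAE elements, fatigue, breast pain, breast shape, arm morbidity and other appendix measures. Changes from baseline are summarised at each follow-up visit. "The comparison of the changes at each time point between the two treatment arms" is to use a paired t-test or a signed rank test. No main time point, significance level, multiplicity rule, baseline covariate or longitudinal model is given.

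**Cosmesis analysis.** Section 16.624 gives frequencies and confidence intervals of "fair or poor cosmesis events at baseline, 2 years, and 5 years by treatment arm". Section 16.2 fixes the same three time points for the patient-rated cosmetic endpoint.

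**Missing forms.** Footnote 7 to section 4.0 says that, for patients who cannot return within the windows, outside records will be sought and quality-of-life forms sent out, "however the required items may not be captured". Under sections 13.1 and 13.2, patients with recurrence or early discontinuation move to event monitoring. In the section 18.1 table only the Patient Status Form is marked for that phase.

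**The concern.** Fatigue, arm function and other patient-reported outcomes are a stated secondary goal (section 2.0). With six unranked comparisons per scale, an isolated significant visit is easy to produce by chance and could be read as an effect of fractionation. With about 36 patients per arm, the choice between a change score and a baseline-adjusted analysis also matters for precision. Finally, a test at one visit uses only the patients with a form at that visit and ignores the earlier scores of those whose forms have stopped.

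The tests named in section 16.623 are for paired data, whereas the arms are independent groups. That is a separate matter. The present point remains after two-sample tests are substituted, and the working below assumes that they have been.

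**Working it through.** **Inputs from the documents.** 72 evaluable patients, 1:1, so 36 per arm (section 16.4); six post-baseline visits (section 4.0); 82 treated to secure 72 evaluable at 24 months, a loss of 10/82 = 12.2% (section 16.4).

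**Assumptions.** Two-sided 0.05 per test; compound symmetry, with correlation r between any two visits (baseline included) of 0.4 to 0.7 and equal variances. The documents give neither alpha nor r.

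**The plan's own figures.** None exists for patient-reported outcomes. The stated power is for the primary endpoint: 80% (10% v 5%) and 41% (10% in both arms). Exact enumeration with 36 per arm, a 10-point margin and a one-sided 95% Wald limit gives 79.4% and 41.7%, so 36 per arm is the right size to use.

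**1. False positives per scale.** Under compound symmetry, two change scores share the baseline. Their covariance is 1 − r and each variance is 2(1 − r), so their correlation is 0.5 whatever r is.

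- Six two-sided 0.05 tests with correlation 0.5: 20.6%.
- Simulated t-tests of change, 36 per arm, r = 0.4 to 0.7: 20–21%.
- Other correlations between the tests: 26.5% if independent (1 − 0.95⁶), 16.5% at 0.7, 10.8% at 0.9.
- A fourth annual visit, as footnote 4 of section 18.1 implies, makes seven tests: 22.9% at correlation 0.5.

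**2. Precision of the 24-month comparison** (variances in units of the single-visit score variance).

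- Change score: 2(1 − r).
- Baseline-adjusted, one visit: 1 − r².
- Baseline-adjusted mean of 12, 24, 36 and 60 months: (1 + 3r)/4 − r².

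| r | one visit, adjusted ÷ change = (1 + r)/2 | 12–60 month mean, adjusted ÷ change = (1 + 4r)/8 |
|---|---|---|
| 0.4 | 0.70 | 0.33 |
| 0.5 | 0.75 | 0.38 |
| 0.6 | 0.80 | 0.43 |
| 0.7 | 0.85 | 0.48 |

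The detectable difference at 80% power is (1.960 + 0.842)·√(2v/36), where v is the variance above. At r = 0.5, v = 1 gives 0.66 SD for the change score and v = 0.75 gives 0.57 SD with baseline adjustment.

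**3. What the repeated-measures model adds at 24 months.** Compared with a single-visit baseline-adjusted analysis, its variance is 0–1% lower with complete data, about 2–4% lower with 12.2% of forms missing at random at each visit, and about 4–9% lower with 25% missing. Nearly all the 24-month gain in step 2 therefore comes from baseline adjustment.

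**4. Cosmesis.** Sections 16.2 and 16.624 use two of six post-baseline ratings. For a baseline-adjusted average over visits, treating the rating as a continuous score, the information lost is 1 − (1 + 6r)/[3(1 + 2r)], which is 37%, 33%, 30% and 28% at r = 0.4, 0.5, 0.6 and 0.7. For change scores it is 1 − (7/6)/(3/2) = 22% at any r.

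**The case against.** These are secondary outcomes of a phase II trial. No alpha and no success claim are attached to them, and the primary result does not depend on them. That stands, and it limits the point to how the patient-reported results are read.

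Several stronger readings are tempting, and the documents do not support them:

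- *About half of the information is thrown away.* Quality-of-life scores from every visit are summarised and compared; they are only not combined. For cosmesis the loss is about 28–37% with baseline adjustment under the assumed r, and 22% with change scores.
- *Only the 2- and 5-year patient ratings are used.* This is uncertain. Section 16.623 takes in the BCTOS subscales and breast shape at each follow-up visit, so BCTOS ratings from other visits may be analysed there. The 2- and 5-year choice in section 16.2 is also explicit.
- *Cosmesis false positives are inflated.* Section 16.624 plans no test.
- *The model is worth a much larger sample.* The large reduction in variance belongs to the 12–60 month average. The 24-month contrast gains far less.
- *Only attenders contribute.* Footnote 7 promises efforts to send forms to patients who cannot return, so absence from clinic need not mean a missing form. No bias can be quantified from the documents.

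It is also fair that one contrast per scale leaves multiplicity across scales. Counting the six groups named in section 16.623 as one scale each, 36 tests become 6, and the expected number of false positives falls from 36 × 0.05 = 1.8 to 6 × 0.05 = 0.3, not to zero.

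**Conclusion.** The concern holds for the quality-of-life analysis. Section 16.623 makes six unranked change-score comparisons per scale. Under two-sided 0.05 and compound symmetry the chance of at least one false-positive visit is about 20% per scale, and 11–26% over the wider range of correlations between tests. The change-score test is also less precise than a baseline-adjusted one: the adjusted 24-month contrast has about 70–85% of its variance, and the adjusted 12–60 month average about 33–48%, for r between 0.4 and 0.7. All these figures rest on the assumed alpha, correlation and covariance structure.

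For cosmesis the finding is limited to under-reporting: two of six post-baseline patient ratings appear in a descriptive analysis, and the overlap with the BCTOS in section 16.623 is unclear. The change is worth making, but nothing here alters the primary conclusion.

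**What to change.** **Section 16.623.** Replace the per-visit tests with one mixed model for repeated measures per scale measured at baseline. Include baseline value, reconstruction factor, arm, visit and arm-by-visit interaction. Name the 24-month arm difference as the main contrast, which matches the timing of the primary endpoint. Give the 12–60 month average as supportive and label other visits descriptive. State the significance level, and state that no adjustment is made across scales if that is the intention. For Breast-Q, use the same model over its observation visits without the baseline term.

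**Section 16.624.** Keep the 2- and 5-year estimates. As an optional supportive analysis, fit a logistic GEE or logistic mixed model to the patients' fair/poor ratings over all section 4.0 visits; a model for continuous scores would not suit a fair/poor outcome. State whether BCTOS ratings are analysed here, under section 16.623, or both.

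**Cost.** SAP wording and modest extra analysis, with no new visits or data. The small downside is the assumption that scores are missing at random given the observed scores. In return, the model uses the earlier scores of patients whose later questionnaires are missing, including those who move to event monitoring.

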16.0 Statistical Considerations and Methodology

This is an open label phase II randomized controlled trial to determine the safety of 15 fraction vs 25 fraction scanning beam proton radiotherapy after mastectomy in patients requiring regional nodal irradiation.

16.1 Primary Endpoint:

16.1.2 Primary endpoint: 24 month complicate rate, defined as the percentage of women randomized who develop one or more of the following events:

- 1) grade 3 or higher late adverse events
- 2) unplanned surgical intervention (not including planned serial fat grafting) in patients who undergo mastectomy with reconstruction.

16.2 Secondary Study Endpoints: The secondary aims of this study are to characterize acute and late adverse events including grade ≥ 2 pneumonitis and reconstruction failure rate, assess patient self-reported cosmesis, evaluate fatigue, breast pain, arm function and other patient reported outcomes, compare the locoregional control, disease free, overall survival. Blood will be collected for future studies exploring dose volume and genomic predictors of adverse cosmesis and biomarkers of cardiotoxicity.

The following definitions are used for the secondary endpoints of interest:

- *Acute adverse events* (up to 90 days post-RT): any adverse event, regardless of attribution, that occurs in the first 90 days post-RT.
- *Late adverse events* (up to 5 years post XRT): any adverse event that occurred after the first 90 days post-RT and up to 5 years post-RT.
- *Reconstruction failure* (up to 5 years post XRT): loss of the tissue expander or implant with the inability to replace it resulting in no final reconstruction or conversion to autologous reconstruction or revised with the addition of autologous reconstruction.[27, 28]
- *Patient Reported Outcomes/Quality of life*: Elements of the Patient-Reported Outcomes Version of the Common Terminology Criteria for Adverse Events (PRO-CTCAE) will be used for patient self-reporting of toxicities. The Breast Cancer Treatment Outcomes Scale (BCTOS) will be used to measure patient reported functional status (pain, mobility). Other measures of fatigue, pain, and arm function are listed in the appendix.
- *Patient self-reported cosmetic outcomes*: the patient self-reported outcome will be assessed using a modified Harvard Cosmesis Scale and a modified BCTOS at baseline, 2 years, and 5 years.

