- *Panel assessed cosmetic outcome*: in addition to patient self-reported and physician reported outcomes, cosmesis will be assessed by a panel of breast cancer medical providers using digital photographs from baseline and at 2 years. The Panel will be blinded to treatment allocation.

- *IBTR*: this is defined as local recurrence from trial registration as a first event at 5 years. IBTR is defined as both invasive and non-invasive breast cancer involving the same breast parenchyma as the original tumor.
- *Regional recurrence*: invasive breast cancer in the axilla, regional lymph nodes, chest wall, and skin of the ipsilateral breast at 5 years.
- *Distant recurrence*: metastatic cancer that has either been biopsy confirmed or clinically diagnosed as recurrent invasive breast cancer at 5 years.
- *Invasive disease free survival*: this is defined as the time from study registration until the occurrence of one of the events in a composite endpoint. This endpoint includes invasive IBTR, regional invasive breast cancer recurrence, distant breast cancer recurrence, death due to any cause, contralateral invasive breast cancer, and second primary non-breast invasive disease.
- *Overall survival*: is defined as the time from registration to death due to any cause.

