16.4 Sample Size Determination

The proposed trial design is a randomized phase II trial with a 1:1 randomization ratio with the stratification variable noted in section 5.1. The primary endpoint for this trial is the 24-month complication rate, as defined above. The study will plan to enroll a total of 72 evaluable patients. An evaluable patient is defined as a patient who receives any dose of the protocol-defined radiotherapy. In this trial, we will accrue and randomize up to 96 patients over 3 years to account for ineligibility, cancellations (withdrawals prior to protocol therapy), major treatment violations, or other reasons, and treat a total of 82 patients in order to ensure 72 evaluable patients at 24 months.

This study is designed as a non-inferiority/superiority “hybrid” design using the approach of Freidlin et al.[36] It is estimated that approximately 2/3 of the patients will undergo reconstruction. For patients who undergo mastectomy with immediate reconstruction, the rate of unplanned surgical complications at the Mayo Clinic is ~15% (personal communications with [name] and [name] 6/2014), comparable to what has been reported in the literature in the modern era.[27]. The rate of grade 3 or greater late toxicity in this population is expected to be $\leq 1\%$ (Whelan ASCO 2011). For the purpose of designing this trial, we will assume a 10% complication rate in the control arm. We consider that a 10% increase of this rate in the experimental arm would be acceptable (i.e. a non-inferiority margin of 10%). Based on the results of the START-B clinical trial[9], it is also plausible that toxicities in the experimental arm may even be reduced with the shortened fractionation schedule. Therefore, a marginal *decrease* in complication rate in the experimental arm to 5% (i.e. marginal benefit margin of 5%) may be reasonably expected. Denote p_0 and p_1 as the 24-month complication rate in the control arm and experimental arm, respectively. The null hypothesis is that the complication rate in the experimental arm is inferior to the control rate of 10% by more than 10% (i.e. $H_0: p_1 - p_0 > 10\%$). The alternative hypothesis is that the complication rate in the experimental arm is non-inferior to the control rate of 10% (i.e. $H_A: p_1 - p_0 < 10\%$).

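### The two surgeons who adjudicate unplanned operations, the source of about 10 in 11 expected primary events, are not stated to be blinded in this open-label trial

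*Combined protocol and SAP*

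**What the plan says.** Section 16.0 describes the design: "This is an open label phase II randomized controlled trial". Section 16.1.2 builds the primary endpoint, the 24-month complication rate, from two components. One is grade 3 or higher late adverse events. The other is "unplanned surgical intervention (not including planned serial fat grafting) in patients who undergo mastectomy with reconstruction".

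Section 11.4 says who decides on the second component: "Unplanned surgical intervention and Reconstruction Failure will be adjudicated by a plastic surgeon and a general surgeon". It does not say whether they are masked to arm, whether they may have treated the patient, what criteria separate planned from unplanned surgery, or how disagreement is settled. The fat-grafting exclusion in 16.1.2 is the only guidance on the word unplanned.

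Blinding is written in at one place only, for the panel that scores cosmesis photographs (Section 16.2): "The Panel will be blinded to treatment allocation".

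Section 16.4 gives the rates behind the design. On reconstruction: "It is estimated that approximately 2/3 of the patients will undergo reconstruction". For patients with immediate reconstruction, "the rate of unplanned surgical complications at the Mayo Clinic is ~15" percent. For the other component, "The rate of grade 3 or greater late toxicity in this population is expected to be" at most 1%. Then: "we will assume a 10% complication rate in the control arm".

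**The concern.** That an operation took place is a fact. Whether it was planned is a judgement, especially in reconstructed patients, who may have staged or revision surgery. In an open-label trial an adjudicator who can see the arm may classify the same operation differently in the two arms, without any intent to do so. The plan protects a secondary endpoint against this and leaves the main component of the primary endpoint without a stated safeguard.

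Events are few: at 36 per arm the plan expects 36 x 10% = 3.6 in the control arm and, if the hoped-for benefit is real, 36 x 5% = 1.8 in the experimental arm. With counts this small, classifying a single operation can decide whether non-inferiority is declared.

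**Working it through.** **Inputs.** Section 16.4: 72 evaluable patients at 1:1, so 36 per arm; control rate 10%; experimental rate 5% or 10%; margin 10 points; one-sided 95% limit. Section 16.61: one-sided 90% interval by normal approximation. The two confidence levels conflict; that is a separate matter, so both are shown.

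**Share of events that depend on the judgement.** Unplanned surgery: 2/3 x 15% = 10.0% of all patients. Grade 3+ late toxicity: at most 1%. Share: 10 / (10 + 1) = 91%, or about 10 of 11 expected control-arm events.

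**Reproducing the plan's power.** With x1 experimental and x0 control events, p1 = x1/36 and p0 = x0/36, the upper limit is

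U = (p1 - p0) + z x sqrt[p1(1 - p1)/36 + p0(1 - p0)/36]

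with z = 1.645 (95%) or 1.282 (90%). Non-inferiority is declared if U does not exceed 10%. Summing the two binomial probabilities over all passing tables at the 95% limit gives 79.4% power at 5% vs 10% and 41.7% at 10% vs 10%. The plan states 80% and 41%, so this method represents the design well.

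**One reclassified operation** (experimental vs control):

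| Limit | Events | U | Result |
|---|---|---|---|
| 95% | 3 vs 4 | -2.78% + 1.645 x 6.98% = 8.7% | pass |
| 95% | 4 vs 4 | 0 + 1.645 x 7.41% = 12.2% | fail |
| 90% | 4 vs 5 | -2.78% + 1.282 x 7.79% = 7.2% | pass |
| 90% | 5 vs 5 | 0 + 1.282 x 8.15% = 10.4% | fail |

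The 95% example does not carry over to the 90% limit, where 4 vs 4 gives 9.5% and passes. The boundary moves by about one event; the sensitivity to one event remains.

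**How often the trial lands there.** This is the probability that adding or removing one event in either arm changes the conclusion:

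| True rates, experimental vs control | 95% limit | 90% limit |
|---|---|---|
| 5% vs 10% | 33% | 22% |
| 10% vs 10% | 37% | 35% |
| 20% vs 10% | 9% | 15% |

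**Effect of biased classification.** The documents give no size for this, so the shift is an assumption. Let the true rates be 20% vs 10%, exactly at the margin, and let a share q of events be called planned. False non-inferiority at the 95% limit:

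| q | Experimental arm only: 20% x (1 - q) vs 10% | Both arms alike: 20% x (1 - q) vs 10% x (1 - q) |
|---|---|---|
| 0 | 5.5% | 5.5% |
| 10% | 8.7% | 7.1% |
| 20% | 13.5% | 9.4% |

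Of the rise of 3.2 points at q = 10%, 1.6 points also appear when both arms are treated alike; at q = 20% it is 3.9 of 8.0 points. Equal leniency lowers event counts against a fixed absolute margin, and blinding would not remove that part. If q applies only to surgical events (19 of the 20 points), the experimental-arm-only figures become 8.5% and 13.0%.

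**The case against.** A reader might infer that the surgeons are unblinded. The documents do not say so: Section 11.4 is silent. Writing blinding in for the cosmesis panel alone makes the inference reasonable but does not prove it. The plan also deserves some credit. It names two adjudicators from two specialties, does not describe them as treating surgeons or radiotherapy investigators, and removes one ambiguous class of surgery by excluding planned serial fat grafting.

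A second tempting reading is that the result will be biased toward non-inferiority. Nothing in the documents supports a direction or a size. An adjudicator sceptical of hypofractionation could push the other way.

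It can also be said that a one-event flip is a property of any small trial with a discrete endpoint and is not evidence of bias. That is right: it measures exposure to bias.

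Finally, masking has limits. Radiotherapy dates can reveal 15 or 25 fractions even when dose and fraction number are removed, and masked adjudication cannot undo any effect of knowing the arm on the decision to reoperate.

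All of this narrows the point. It does not remove it, because silence in an open-label trial permits unmasked review of the judgement that carries most of the primary endpoint.

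**Conclusion.** The point holds as a cheap improvement. The documents support three things: the adjudicators are not stated to be blinded, about 10 of 11 expected primary events pass through their judgement, and one reclassified operation changes the conclusion near the boundary under either confidence level. On the plan's two power scenarios the chance of landing there is about one in three at the 95% limit and 22% to 35% at the 90% limit.

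The false non-inferiority figures of 8.7% and 13.5% rest on assumed shifts of 10% and 20%, true rates at the margin, 36 per arm and the 95% limit. They show what unmasked classification could do and do not forecast what it will do. Only about half of the rise is attributable to treating the arms differently. The stated sample size and power are unaffected.

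**What to change.** In Sections 11.4 and 16.1.2, state that the same two adjudicators:

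- did not treat the patient;
- review operative and clinic records with arm, dose, fraction number and radiotherapy dates redacted;
- apply a written planned/unplanned rule fixed before review, including how disagreement is resolved.

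In Section 16.61, add a sensitivity analysis of the arm difference that counts all reoperations other than planned serial fat grafting. It will include planned stages of reconstruction, so its rates will not be comparable with the 10% design assumption. Its use is to show whether the planned/unplanned call drives the result.

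The cost is a few sentences plus redaction of records for the patients who are reoperated. They come from about 48 reconstructed patients (2/3 x 72 evaluable) to about 55 (2/3 x 82 treated). No extra assessors or patients are needed. Masking may be imperfect, and the change does not address any influence of the arm on the decision to operate; the trial report should say so.
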